4.3 Sample Size

Approximately 210 subjects will be equally allocated to five treatment groups and the placebo group, representing a randomization ratio of 1:1:1:1:1. The sample size for this study is based on the expected proportion of subjects who achieve endoscopic remission at Week 12/16 and on the expected proportion of subjects who achieve clinical remission at Week 16. Assuming an endoscopic remission (as well as clinical remission) rate of 12% in the placebo arm and maximum of 35% in at least one of the ABT-494 BID treatment arms (3 mg BID, 6 mg BID, 12 mg BID and 24 mg BID) at Week 12/16, a sample size of 35 subjects per treatment group is sufficient to test for the presence of a dose response signal, to select the best dose response model for the observed data out of a prespecified set of candidate models, and to estimate target doses of interest (e.g., the minimum effective dose, MED) via modeling using MCP-Mod (Multiple comparison procedure and modeling) approach. This approach provides at least 80% average power to detect a dose effect at 5% level of significance (one-sided) with the linear, E_{max} , exponential, logistic, and sigEmax models pre-specified as likely candidates to characterize the dose-response for ABT-494 for the two co-primary endpoints of clinical and endoscopic remission.

5.0 Analysis Populations

5.1 Definition for Analysis Populations

The following populations will be used for analyses in the study:

The modified intent-to-treat (MITT) analysis set includes all randomized subjects who have taken at least one dose of study drug in the double-blind induction period. For the MITT analysis set, subjects are assigned to a treatment group based on the randomization schedule, regardless of the treatment actually received. The MITT population will also be referred as "All Randomized and Treated Subjects." The MITT analysis set will be used for all efficacy analysis for the double-blind induction period and baseline demographic and characteristics analyses.

The safety analysis set consists of all subjects who received at least one dose of study medication. For the safety analysis set, subjects are assigned to a treatment group based on the treatment actually received, regardless the treatment randomized.

5.2 Variables Used for Stratification of Randomization

At Baseline, subjects will be randomized in a 1:1:1:1:1:1 ratio to receive one of the six treatment groups (double-blind ABT-494 induction doses or matching placebo).

The following are the treatment groups:

Group 1: ABT-494 3 mg BID

Group 2: ABT-494 6 mg BID

Group 3: ABT-494 12 mg BID

Group 4: ABT-494 24 mg BID

Group 5: ABT-494 24 mg QD

Group 6: Placebo

The randomization at Baseline will be stratified by endoscopic disease severity (SES-CD < 15 and \geq 15), prior anti-TNF use (naïve and experienced), and by participation in the substudy of the gene expression in intestinal biopsies (Yes and No). As part of the randomization at Baseline, subjects will be randomly assigned (1:1) to have their follow-up ileocolonoscopy done at Week 12 or Week 16.

At Week 16, subjects who have completed the induction period will be re-randomized in a ratio of 1:1:1 to one of the three double-blinded doses of ABT-494 3 mg BID, 6 mg BID or 12 mg BID. The re-randomization will be stratified by dose received during the first 16 weeks, and overall response (responder versus non-responder) at Week 16. The

subjects who were re-randomized at Week 16 to ABT-494 24 mg QD prior to Protocol Amendment 2 will continue to receive the same double-blind dose until Week 52/PD.

Overall response consists of both Endoscopic response and Clinical response. The central reader endoscopic score will be used for calculating the Endoscopic response for the evaluation of the efficacy endpoints. However, for stratification re-randomization, the endoscopic score at baseline from central reader and the endoscopic score at Week 12 or Week 16 from site local reader will be used in order to determine response status.

6.0 Analysis Conventions

Definition of Baseline for Induction Period

The Baseline visit date for Induction Period is the date when the first dose of study drug is received and referred to as Day 1 or Week 0. The Baseline value for a variable is defined as the last non-missing value on or before the date of the first dose of study drug.

Definition of Rx Days (Days Relative to the First Dose of Study Drug)

Rx Days are calculated for each time point of interest and it provides a quantitative measure of days between the event and the first dose date. That is, the Rx Day is calculated as the event date minus the date of first dose of study drug plus 1. The Rx Day will be a negative value when the time point of interest is prior to the date of first dose of study drug, and the Rx Day will be a positive value when the time point of interest is after the first dose date. By this calculation algorithm the first dose day is Rx Day 1, while the day prior to the date of first dose is defined as Rx Day –1 (there is no Rx Day 0). Rx Days are used to map actual study visits to the protocol specified study visits.

Definition of Analysis Windows

Since subjects do not always adhere to the study visit schedule, the following rules will be applied to assign actual visits to protocol-specified visits including early termination visits. For each study visit mentioned in the protocol, a nominal or target day will be selected to represent the corresponding visit along with a window around the target day.

Windows will be selected in a non-overlapping fashion so that a date collected on the CRF does not correspond to multiple visit windows. Moreover, windows will not discard any Post-Baseline measurement recorded on the CRF. If a subject had two or more actual visits in one visit window, the visit closest to the scheduled visit will be used as the study visit for that window. If two visits are equidistant from the target, then the later visit will be used for reporting. If more than one assessment is collected on the same day, then the average of those assessments will be used in analyses.

Table 2. Visit Windows for Analysis of Efficacy Variables (Except SES-CD, IBDQ, WPAI, Abdominal Pain Rating Scale), Laboratory Parameters and Vital Signs for 16-Week Double-Blind Induction Period

| Scheduled Week | Nominal Day | Time Window (Rx Day Range) |
|----------------|----------------|-------------------------------|
| Week 0 | 1 ^a | ≤ 1 |
| Week 2 | 15 | 2 – 22 |
| Week 4 | 29 | 23 – 43 |
| Week 8 | 57 | 44 – 71 |
| Week 12 | 85 | 72 – 99 |
| Week 16 | 113 | 100 – 999 ^b |

Rx Day A = date of visit – date of first study drug in double-blind induction period + 1.

- a. Day of first dose of study drug in double-blind induction period.
- b. Rx Day 999 or first dose of extension period, whichever earlier.

Table 3. Visit Windows for Analysis of IBDQ, EQ5D, and WPAI for 16-Week Double-Blind Induction Period

| Scheduled Week | Nominal Day | Time Window (Rx Day Range) |
|----------------|----------------|-------------------------------|
| Week 0 | 1 ^a | ≤ 1 |
| Week 8 | 57 | 2 – 85 |
| Week 16 | 113 | 86 – 999 ^b |

Rx Day A = date of visit – date of first study drug in double-blind induction period + 1.

- a. Day of first dose of study drug in double-blind induction period.
- b. Rx Day 999 or first dose of extension period, whichever earlier.

Table 4. Visit Windows for Analysis of SES-CD and Abdominal Pain Rating Scale for 16-Week Double-Blind Induction Period

| Scheduled Week | Nominal Day | Time Window (Rx Day Range) |
|----------------|----------------|-------------------------------|
| Week 0 | 1 ^a | ≤ 1 |
| Week 12 | 85 | 2 – 99 |
| Week 16 | 113 | 100 – 999 ^b |

Rx Day A = date of visit – date of first study drug in double-blind induction period + 1.

a. Day of first dose of study drug in double-blind induction period.

b. Rx Day 999 or first dose of extension period, whichever earlier.

Table 5. Visit Windows for Analysis of Fecal Calprotectin for 16-Week Double-Blind Induction Period

| Scheduled Week | Nominal Day | Time Window (Rx Day Range) |
|----------------|----------------|-------------------------------|
| Week 0 | 1 ^a | ≤ 1 |
| Week 4 | 29 | 2 – 71 |
| Week 16 | 113 | 72 – 999 ^b |

Rx Day A = date of visit – date of first study drug in double-blind induction period + 1.

a. Day of first dose of study drug in double-blind induction period.

b. Rx Day 999 or first dose of extension period, whichever earlier.

CD-Related Corticosteroid Use

Subjects in whom the CD-related corticosteroids (systemic or rectal corticosteroids) that were not being taken at Baseline and are initiated during the study or who have equivalent dose of these medications increased to greater than the dose taken at Baseline will be censored for efficacy assessments (i.e., will be considered non-responders for categorical endpoints and will have Baseline values carried forward for non-categorical assessments) from that point through the end of the study. These subjects will continue to be evaluated in the safety population.

The equivalent steroid dose will be determined based on the table below:

| Corticosteroid | Equivalent Dose (mg) |
|--------------------|----------------------|
| Cortisone | 25 |
| Hydrocortisone | 20 |
| Prednisone | 5 |
| Prednisolone | 5 |
| Triamcinolone | 4.0 |
| Methylprednisolone | 4.0 |
| Betamethasone | 0.75 |
| Dexamethasone | 0.75 |
| Budesonide | 1 |
| Beclomethasone | 5 |
| Beclometasone | 5 |

Definition of Missing Data Imputation

The following imputation methods will be used to impute missing values in the efficacy analyses. In addition, an observed case analysis will be performed.

Non-Responder Imputation (NRI)

The NRI approach is used for binary efficacy variables. These variables can take values of 'Achieved' or 'Not Achieved' or may be missing for any reason including discontinuation from study. According to the NRI imputation approach, all missing values will be considered as 'Not Achieved.'

Last Observation Carried Forward (LOCF)

For all variables (categorical variables and continuous variables), the following rules will be used for the LOCF approach:

1. Baseline and Pre-Baseline values will not be used to impute the missing Post-Baseline values.

2. Missing values after Study Day 1 will be imputed using the latest non-missing values after Day 1 and prior to the missing value. If there are no non-missing values after Baseline, then the LOCF value will be missing.

Observed Case (OC)

Observed case analysis will be performed such that missing values will not be imputed.

However, all observed values will be replaced by Baseline value once subjects received CD-related corticosteroid therapy.

Mixed-Effect Model Repeated Measure (MMRM)

The MMRM model will be used for continuous efficacy variables with longitudinal data as the primary analysis. The MMRM model includes the baseline values as covariate; randomization strata, treatment, time point and treatment-by-time point interaction as fixed effects; and subjects within treatment as random effect. An unstructured (co)variance structure will be used to model the within-subject error. The comparison at a time point will be the contrast between treatments at that time point. Satterthwaite's approximation will be used to estimate denominator degrees of freedom.

Imputation of Missing Dates

For Baseline, efficacy, and safety parameters, if the day and/or month are missing, the following conventions will be used to impute the missing dates:

- 01 for missing start day
- End of month for missing end day
- January 1st for missing start month
- December 31st for missing end month

In case of partially missing AE start and stop dates, the dates will be imputed by comparing to first dose date of study medication so that the corresponding AEs will be

made treatment-emergent whenever possible. If the start date of an AE is partially missing and the month is the same as the start date of a new therapy, the AE will be made treatment emergent to the new therapy.

In case of missing or partially missing study drug dosing dates, the dates will not be imputed. Subjects will be treated as not receiving dose on that date.

Rule for CDAI Calculation

Up to 14 days of diary entries will be evaluated from the ePRO tool for the CDAI calculation for each visit. The diary entries on the days the subjects receive endoscopy preparation medications, the day of endoscopy procedure, and 2 days after endoscopy procedure will be excluded. For each CDAI subscore, the available scores from the most recent diary days (at least 4 days, up to 7 days) prior to actual day of the study visit will be summed, and then multiplied by the corresponding multiplier to get subtotal score. If available diary entries are fewer than 7 days, the subtotal score will be calculated as (summed total available score/number of days) \times 7 \times corresponding multiplier. The three subtotal scores that are based on ePRO (number of liquid/very soft stools, abdominal pain rating, and general well-being) will then be rounded to one decimal. The final CDAI is rounded to a whole number.

If a subject has less than 4 days of diary data, the total CDAI score will not be calculated and will be considered missing.

Same rule will be applied to average daily stool frequency and average daily abdominal pain.

Bristol Stool Chart

Up to 14 days of diary entries will be evaluated from the ePRO tool for the Bristol Stool Chart calculation. These assessments on the day of endoscopy procedure, the day before endoscopy procedure (due to preparation medications), and 2 days after endoscopy procedure are excluded. The 7 most recent non-missing assessments will be used for the

analysis. The Bristol Stool Chart is calculated as the number of days the subjects with Type 6 or Type 7 divided by the total number days with non-missing assessments, rounded to two decimal.

If a subject has less than 4 days of diary data, the Bristol Stool Chart will not be calculated and will be considered missing.

If a subject achieved reduction from Baseline $\geq 50\%$, this subject will be classified as Responder.

SES-CD Scoring

All colonoscopies shall be performed and recorded in video format. To be eligible for the study, the screening colonoscopy may be performed during the Screening Period (or up to 45 days before the Baseline visit if Amendment 2 is in place at the site). Colonoscopies will also be performed at the Week 12 or 16 visit. Investigators shall provide their SES-CD score assessment on the SES-CD score sheet for the baseline and Week 12 or 16 visits. The investigator SES-CD scores are to be entered in the appropriate eCRF, however neither the Investigator's Baseline nor Week 12 or 16 SES-CD scores will be used for the study's efficacy analyses.

All videotaped colonoscopies will undergo central review. One primary central reviewer will evaluate the videotaped colonoscopies and provide the SES-CD scores to Parexel. A second central reviewer will adjudicate between the investigator's and the central reviewer's SES-CD scores if there is discrepancy (more than 10% difference) in total SES-CD score. The adjudicator will select the final SES-CD score that he/she most agrees with from those provided by the investigator and the central reviewer, and this final SES-CD score will be entered into the study database and be used for the study's efficacy analyses. If there is no discrepancy between the investigator and the central reviewer, that central reviewer's score will be entered into the study database and serve as the SES-CD score to be used for the study's efficacy analyses.

If there is a missing SES-CD individual variable in the SES-CD score that serves as the SES-CD score for the study's efficacy analyses (for all variables except the "Presence of Narrowing" variable), the following imputation rules will be applied:

If the same individual variable is:

- Missing at both Baseline and Week 12 or 16: the missing value will be imputed as zero at both time points, and no change will be assumed.
- Present at Week 12 or 16 but missing at Baseline: the missing Baseline value will be imputed based on the value given at Week 12 or 16, and no change will be assumed.
- Present at Baseline but missing at Week 12 or 16: the missing Week 12 or 16 value will be imputed based on the value given at Baseline and no change will be assumed.

If there is a missing SES-CD "Presence of Narrowing" individual variable in the SES-CD score that serves as the SES-CD score for the study's efficacy analyses, the following imputation rules will be applied:

If the Presence of Narrowing individual variable is:

- Missing at both Baseline and Week 12 or 16: the missing Presence of Narrowing individual variable will be imputed as zero and no change will be assumed.
- Present at Week 12 or 16 but missing at Baseline: the missing Baseline value will be imputed based on the individual variable given at Week 12 or 16 and no change will be assumed.

However, if there is a Baseline individual variable (for any SES-CD subscore) for intestinal segments proximal to (above) the segment with the missing Presence of Narrowing individual variable, the maximum imputed value for the missing Presence of Narrowing individual variable will be 2.

- Present at Baseline but missing at Week 12 or 16: the missing Week 12 or 16 value will be imputed based on score given at Baseline and no change will be assumed.

However, if there is a Week 12 or 16 individual variable is present for intestinal segments proximal to (above) the segment with the missing Presence of Narrowing variable, the maximum imputed value for the missing Presence of Narrowing individual variable will be 2.

(Gastrointestinal anatomy places the ileum proximal to the right colon, which is proximal to the transverse colon, which is proximal to the sigmoid and left colon, which is proximal to the rectum.)

A sensitivity analysis (Worst Case Imputation) will be performed by imputing all missing Baseline individual variables as '0' and all missing Week 12 or 16 variables as '3' except the Week 12 or 16 Presence of Narrowing individual variable. At Week 12 or 16, the worst values for Presence of Narrow individual variable will be 2 for Rectum, Sigmoid and Left Colon, Transverse Colon, and Right Colon, and 3 for Ileum.

If a subject only has Baseline SES-CD, and no post-Baseline SES-CD, all Baseline missing individual variables will be imputed as zero.

Isolated Ileal Crohn's Disease at Baseline

Isolated Ileal Crohn's disease at Baseline is defined as all individual variables for Rectum, Sigmoid and Left Colon, Transverse Colon, and Right Colon are zero at Baseline and subscore for ileal ≥ 4 . If any of the individual variables is missing or not zero, this subject is classified as Not Isolated Ileal Crohn's disease at Baseline.

Definition of Endoscopic Remission

SES-CD ≤ 4 and at least two point reduction versus Induction baseline and no subscore > 1 in any individual variable.

Definition of Endoscopic Response

SES-CD at least 25% reduction from Induction baseline.

Definition of Clinical Remission

Average daily stool frequency ≤ 1.5 and not worse than baseline AND average daily abdominal pain ≤ 1.0 and not worse than Induction baseline.

Definition of Clinical Response

Average daily stool frequency at least 30% reduction from Induction baseline and average daily abdominal pain not worse than Induction baseline OR average daily abdominal pain at least 30% reduction from Induction baseline and average daily stool frequency not worse than Induction baseline.

Definition of Remission

Remission at Week 16 is defined as both Endoscopic remission at Week 12/16 AND Clinical remission at Week 16.

Definition of Response

Response at Week 16 is defined as both Endoscopic response at Week 12/16 AND Clinical response at Week 16.

Definition of Modified Clinical Remission

Average daily stool frequency ≤ 2.8 and not worse than baseline AND average daily abdominal pain ≤ 1.0 and not worse than Induction baseline. This endpoint will only be analyzed among subjects with baseline average daily stool frequency ≥ 4 or average daily abdominal pain ≥ 2.0 .

EuroQol-5D-5L (EQ-5D)

EQ-5D is a standardized measure of health status developed by the EuroQol Group in order to provide a simple, generic measure of health for clinical and economic appraisal.

The EQ-5D consists of 2 pages. The first page measures 5 dimensions of the health status (mobility, self-care, usual activities, pain/discomfort, and anxiety/depression) with 5 levels per dimension (no problems, slight problems, moderate problems, severe problems, and unable corresponding to Level 1 to Level 5 respectively). The second page is an EQ Visual Analogue Scale (EQ VAS). EQ-5D health states, defined by the EQ-5D-5L descriptive system on the first page, may be converted into a single index value. The change from baseline of the index value and EQ VAS will be analyzed and reported. UK scoring algorithm will be used ([Table 6](#)).

Table 6. An EQ-5D-5L Value Set for England

| | Central Estimate | Value for Health State 23245 |
|--|---|------------------------------|
| Mobility | | |
| No Problem | 0 | |
| Slight | 0.051 | 0.051 |
| Moderate | 0.063 | |
| Severe | 0.212 | |
| Unable | 0.275 | |
| Self-Care | | |
| No Problem | 0 | |
| Slight | 0.057 | |
| Moderate | 0.076 | 0.076 |
| Severe | 0.181 | |
| Unable | 0.217 | |
| Usual Activities | | |
| No Problem | 0 | |
| Slight | 0.051 | 0.051 |
| Moderate | 0.067 | |
| Severe | 0.174 | |
| Unable | 0.190 | |
| Pain/Discomfort | | |
| No | 0 | |
| Slight | 0.060 | |
| Moderate | 0.075 | |
| Severe | 0.276 | 0.276 |
| Unable | 0.341 | |
| Anxiety/Depression | | |
| Not | 0 | |
| Slight | 0.079 | |
| Moderate | 0.104 | |
| Severe | 0.296 | |
| Unable | 0.301 | 0.301 |
| The value for health state 23245: 1 – 0.9675 × (sum of the subscores) | $1 - 0.9675 \times (0.051 + 0.076 + 0.051 + 0.276 + 0.301) = 0.270$ | |

The index value is $1 - 0.9675 \times$ sum of 5 components based on central estimates.

The minimum index value is – 0.281 (health state 55555), and the maximum index value is 1 (health state 11111). (Reference: Devlin N et al. Valuing health-Related Quality of Life: Ann EQ-5D-5L Value Set for England, January 2016 –

<https://www.ohe.org/publications/valuing-health-related-quality-life-eq-5d-5l-value-set-england> or <http://www.euroqol.org/about-eq-5d/valuation-of-eq-5d/eq-5d-5l-value-sets.html>).

If one of the 5 dimensions is missing, the EQ-5D index value will be missing.

7.0 Demographics, Baseline Characteristics, Medical History, and Previous/Concomitant Medications

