#### **5.2.3.2        Concomitant Therapy**

Subjects who enter the study on aminosalicylates and/or MTX must remain on stable dose of this therapy for the entire study period.

Subjects who enter the study on Crohn's disease related antibiotics must remain on stable doses of this medication for at least 14 days prior to Baseline. Change in dose of Crohn's disease related antibiotics during the study will not be allowed for the 16-week induction

---

period, except in cases of treatment related toxicity or concerns about development of antibiotic resistance.

Subjects who enter the study on oral corticosteroids are not allowed to change the corticosteroid dose during the first 2 weeks of the treatment period. At Week 2, subjects who are taking corticosteroid therapy at Baseline must have their corticosteroid therapy tapered according to a tapering schedule specified below and in Section [5.3.1.1](#).

A proposed schedule to taper prednisone dose starts with a weekly decrease by 5 mg/day prednisone (or equivalent) for doses > 10 mg/day of prednisone (or equivalent) until a 10 mg/day (or equivalent) dose is reached, then a weekly decrease by 2.5 mg/day (or equivalent) until discontinuation.

A proposed schedule to taper budesonide dose starts with a weekly decrease by 3 mg budesonide until discontinuation.

If a subject should experience an inadequate response during the corticosteroid taper, the subject may have their corticosteroid dose increased per the investigator's discretion up to and beyond the dose used at Baseline. Subjects in whom the maximum steroid dose exceeds the dose used at Baseline will be considered non-responders and will be censored for efficacy assessments from that point forward through the end of the study. These subjects will continue to be evaluated in the safety population.

Use of inhaled or topical dermatologic corticosteroids is not restricted.

Subjects who enter the study on probiotics may continue this therapy provided doses remain stable from Baseline throughout the duration of the study.

Setons are authorized as concomitant therapy in subjects with perianal fistulas and should be documented in the CRF under concomitant medications.

The AbbVie Study Designated Physician identified in Section [6.1.5](#) should be contacted if there are any questions regarding concomitant or prior therapy(ies).

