#### **8.1.3 Definition of Missing Data Imputation**

Missing data will be imputed using one or more of the following methods:

**Last Observation Carried Forward (LOCF):** The LOCF analyses will use the completed evaluation from the previous visit for efficacy measures assessed to impute missing data at later visits.

**Non-Responder Imputation (NRI):** In NRI analyses, subjects who prematurely discontinue the study prior to endoscopic assessment at Week 12/16 will be considered non-responders with respect to endoscopic remission.

**Observed Cases (OC):** The OC analysis will not impute values for missing evaluations, and thus a subject who does not have an evaluation on a scheduled visit will be excluded from the OC analysis for that visit.

The stool frequency and abdominal pain scores at an assessment visit (e.g., Week 12, Week 16) will be the average of the daily values reported during the 7 usable days preceding the scheduled assessment visit.

If 7 days daily values are not available, an average will be calculated based on the number of days with available data as follows:

- An average for the most recent 6 days will be calculated if data for only 6 days are available,
- An average for the most recent 5 days will be calculated if data for only 5 days are available,
- An average for the most recent 4 days will be calculated if data for only 4 days are available.

Diary entries should not be included in the 7 days evaluated prior to the visit if: (1) the day the subject received medication for bowel preparation prior to endoscopy, (2) the day the subject underwent an endoscopy, and (3) 2 days following the endoscopy. Earlier diary entries will be used accordingly in order to provide the most recent data for 7 days prior to the respective study visit.

If the minimum number of days of diary data (i.e., 4 days for SF and AP) are not available, then the subject's score for that visit will be considered missing and NRI will be used for any endpoints (e.g., clinical remission) relating to data for this visit. Subjects who discontinue prior to Week 16 for any reason will be considered as "not-achieved" for clinical remission endpoint.

**Mixed Imputation:** Subjects who discontinue prior to Week 16 due to lack of efficacy or adverse events will be considered as "not achieved" for the clinical remission. Subjects who discontinue for other reasons will be categorized according to LOCF.

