A subject will be considered a failure for the efficacy analyses at a later time points after the corticosteroid dose has been increased to greater than the dose at Baseline.

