For all variables (categorical variables and continuous variables), the following rules will be used for the LOCF approach:

1. Extension Baseline and Pre-Baseline values will not be used to impute the missing Post-Baseline values.
2. Missing values after Study Day 1 will be imputed using the latest non-missing values after Day 1 and prior to the missing value. If there are no non-missing values after Baseline, then the LOCF value will be missing.

Observed Case (OC)

Observed case analysis will be performed such that missing values will not be imputed. However, all observed values will be replaced by Induction Baseline value once subjects received CD-related corticosteroid therapy, or value prior to open label therapy once subjects moved to open-label therapy.

Mixed-Effect Model Repeated Measure (MMRM)

The MMRM model will be used for continuous efficacy variables with longitudinal data as the primary analysis. The MMRM model includes the baseline values as covariate, treatment, time point and treatment-by-time point interaction as fixed effects; and subjects within treatment as random effect. An unstructured (co)variance structure will be used to model the within-subject error. The comparison at a time point will be the contrast between treatments at that time point. Satterthwaite's approximation will be used to estimate denominator degrees of freedom.

Imputation of Missing Dates

For Baseline, efficacy, and safety parameters, if the day and/or month are missing, the following conventions will be used to impute the missing dates:

- 01 for missing start day

- End of month for missing end day
- January 1st for missing start month
- December 31st for missing end month

In case of partially missing AE start and stop dates, the dates will be imputed by comparing to first dose date of study medication so that the corresponding AEs will be made treatment-emergent whenever possible. If the start date of an AE is partially missing and the month is the same as the start date of a new therapy, the AE will be made treatment emergent to the new therapy.

In case of missing or partially missing study drug dosing dates, the dates will not be imputed. Subjects will be treated as not receiving dose on that date.

Rule for CDAI Calculation

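### The observed-case rule in both SAPs is triggered by any receipt of Crohn's steroids, which contradicts the SAPs' own narrower steroid rule and, read literally, makes every baseline steroid user a failure in that analysis

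*SAP*

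**What the plan says.** Section 6.0 of each SAP holds two steroid triggers.

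- **CD-Related Corticosteroid Use.** The Induction SAP censors subjects for efficacy in two cases: the steroids are ones "that were not being taken at Baseline and are initiated during the study", or the subjects are those "who have equivalent dose of these medications increased to greater than the dose taken at Baseline". From that point they are non-responders for categorical endpoints, and other measures take the Baseline value. The Extension SAP has the same two limbs.
- **Observed Case.** After saying that missing values stay missing, the Induction SAP adds: "However, all observed values will be replaced by Baseline value once subjects received CD-related corticosteroid therapy". The Extension SAP says "all observed values will be replaced by Induction Baseline value once subjects received CD-related corticosteroid therapy", and adds a second replacement for subjects who move to open-label therapy. Neither steroid clause mentions starting a steroid or exceeding the Baseline dose, and neither refers back to the steroid rule.

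Protocol 8.1.3 defines OC without any steroid replacement: "The OC analysis will not impute values for missing evaluations". Its steroid failure rule applies only "after the corticosteroid dose has been increased to greater than the dose at Baseline". On conduct, Protocol 5.2.3.2 states "Subjects who enter the study on oral corticosteroids are not allowed to change the corticosteroid dose during the first 2 weeks" of treatment; tapering follows.

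Induction SAP 10.2 names OC as a sensitivity analysis for both co-primary endpoints. For endoscopic remission it is the only one listed there. Elsewhere OC rests on a general line in Section 6.0 of each SAP.

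**The concern.** A subject who enters on oral steroids keeps taking them for at least two weeks on study, and so has received such therapy before the first post-baseline visit. Under the literal OC trigger that subject's whole post-baseline record becomes Baseline. Under the steroid rule in the same section, the same subject keeps every observed value unless the dose rises above Baseline.

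The sentence can yield three different datasets: replacement after any receipt, after a new start only (which misses dose increases), or after a new start or a dose above Baseline. Induction SAP 3.0 says the document is there to guide programming, so two competent programmers could follow it and disagree.

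At stake is what the OC analysis can show. It is meant to test whether the co-primary result depends on treating missing subjects as failures. Under the literal trigger it also fails subjects who have complete data and are tapering as the protocol requires. A weaker OC result could then be mistaken for sensitivity to missing data.

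**Working it through.** **1. The planning figure.** The sample size sections (Protocol 8.2; Induction SAP 4.3) assume 12% remission on placebo, a maximum of 35% in at least one BID arm, 35 per group and one-sided 5%, and state at least 80% average MCP-Mod power. The candidate shape parameters are not given, so three sets were assumed, for placebo and the four BID doses on the logit scale:

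| Set | Emax ED50 | Exponential δ | Logistic ED50, δ | sigEmax ED50, h | Average power |
|---|---|---|---|---|---|
| 1 | 6 | 12 | 12, 3 | 8, 3 | 83.2% |
| 2 | 3 | 8 | 8, 2 | 6, 4 | 82.8% |
| 3 | 12 | 20 | 12, 5 | 12, 2 | 83.2% |

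The stated figure is reproduced. The textual point does not rest on it; it is the reference for step 4.

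**2. Who meets each trigger.**

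| Subject | Steroid rule (6.0) | Protocol failure rule | Literal OC sentence |
|---|---|---|---|
| On steroid at Baseline, tapers | no | no | yes |
| On steroid at Baseline, exceeds Baseline dose | yes | yes | yes |
| Not on steroid, starts on study | yes | yes (above a Baseline dose of zero) | yes |
| Never on steroid | no | no | no |

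The rules part only in the first row. The literal trigger has no end, so a completed taper does not lift it. Entry is capped at 30 mg/day prednisone. On the proposed schedule, (30 − 10)/5 = 4 weekly steps reach 10 mg and 10/2.5 = 4 more reach zero. With the first step at Week 2, the eighth is at Week 9. Such a subject could be off steroids well before Week 12 or 16 and still be set to Baseline.

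**3. Can a Baseline value count as success?** Not for an eligible subject:
- Clinical remission needs stool frequency ≤ 1.5 and abdominal pain ≤ 1.0; entry needs ≥ 2.5 or ≥ 2.0 respectively, so at least one component fails.
- Endoscopic remission needs a fall of at least 2 points; replacement makes the change 0.
- CDAI < 150 fails because entry needs CDAI ≥ 220.

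Every baseline user is therefore not achieved in OC. The steroid-free endpoints are defined only among baseline users, so any OC version of them would be 0% in every arm.

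**4. Size in OC.** Let s be the share of baseline users. The documents plan to tabulate it but give no value, so 20% to 60% is assumed. Assume also that s is equal across arms, that users and non-users have the same underlying remission rates, and that nothing is missing. Then

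OC rate = (1 − s) × p + s × 0, and OC difference = (1 − s) × (35 − 12).

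Pairwise power is Φ{[Δ − 1.645√(2p̄(1−p̄)/n)] / √[(p₀(1−p₀)+p₁(1−p₁))/n]} with n = 35; MCP power uses shape set 1.

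| s | Overwritten of 210 | Placebo | Best arm | Difference (points) | Pairwise power, one-sided 5% | Average MCP power |
|---|---|---|---|---|---|---|
| 0% | 0 | 12.0% | 35.0% | 23.0 | 74% | 83% |
| 20% | 42 | 9.6% | 28.0% | 18.4 | 63% | 74% |
| 40% | 84 | 7.2% | 21.0% | 13.8 | 51% | 61% |
| 60% | 126 | 4.8% | 14.0% | 9.2 | 37% | 45% |

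In the last row placebo has about 0.048 × 35 = 1.7 expected remissions, so the power figures there are rough. With the narrower trigger, baseline users at or below their Baseline dose keep their data and the s = 0 row applies.

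**The case against.** The best defence is context. The OC sentence follows shortly after the steroid rule and repeats its consequence, Baseline carried forward. Speaking of the time once a subject received therapy suggests an event on study. In the Extension SAP the two OC replacements match the two censoring rules one for one. The protocol states the above-Baseline trigger repeatedly, and the Induction SAP plans steroid-free endpoints and a subgroup by baseline steroid use, which makes little sense if every baseline user is a failure.

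Much of this stands: the sentence is probably shorthand for the rule above it. But baseline users do receive steroid on study, there is no cross-reference, and in the Extension SAP the open-label clause keeps its parent rule's trigger while the steroid clause drops its qualifiers. Probable intent does not remove the conflict.

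Three stronger readings are tempting, and the documents do not support them:
- **That the MMRM is affected.** A reader might infer that observed values feed the MMRM, which is primary for continuous endpoints. OC and MMRM are separate headings, the replacement sentence stands only under OC, and no MMRM text in either SAP refers to OC-replaced data.
- **That the primary result is affected.** The co-primary analysis uses non-responder imputation with the narrower steroid rule.
- **That data were in fact overwritten.** The documents do not show how the sentence was programmed.

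The reach beyond the co-primaries is also thin. For secondary and extension endpoints the efficacy sections name non-responder imputation and LOCF, not OC, and the Extension SAP analyses no co-primary endpoint.

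**Conclusion.** The point holds as a contradiction in the wording of an analysis rule. In both SAPs the OC trigger is wider than the steroid rule in the same section and than the protocol's failure rule. Taken as written, it turns every baseline steroid user into a failure in the OC sensitivity analysis of both co-primary endpoints.

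The dilution to 18.4 points at a 20% share and 9.2 points at 60% is an illustration. It rests on an undocumented steroid share, on equal shares and remission rates across the groups compared, and on the plan's maximum effect, which is assumed for at least one BID arm and not for all. Baseline steroid use is not a stratification factor, so unequal shares by chance could move the OC difference either way. The size applies to OC alone; the point is worth correcting because the analysis is named and the correction is small.

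**What to change.** **Extension SAP.** In the OC paragraph, tie the steroid replacement to the CD-Related Corticosteroid Use rule in the same section: values are replaced from the point at which a subject starts a CD-related steroid not taken at Baseline, or exceeds the Baseline equivalent dose. Leave the open-label clause as it is. The cost is one clause.

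**Induction SAP.** Extension SAP 3.0 says that it was signed before the December 2016 induction lock, so this cannot be a simple edit. Record the same clarification, for example in a note to file and in the study report. Confirm from the programs which trigger was used. If it was the literal one, rerun the OC sensitivity analyses of the two co-primary endpoints and any other OC tables, and report them as corrected. If the narrower one was used, a sentence saying so is enough.

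This applies the SAPs' own rule to the OC dataset. It changes no treatment, no data collection and no primary analysis.
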